In the Single-Dose Phase, as each treatment cohort of subjects within each age group is completed, the effectiveness, safety, and tolerability will be assessed by the IDMC before enrolling subjects into the next-higher treatment cohort. The IDMC will also provide recommendation on whether the subsequent treatment cohorts are needed in the Single-Dose Phase (up to 3 treatment cohorts in total may be tested in the Single-Dose Phase). If needed, non-oxycodone, non-oxymorphone rescue analgesia will be available according to SOC at each institution. Blood from a patent line (see section 12.4.1) will be collected to assess pharmacokinetics, examine dose proportionality, and estimate effective and safe dosing. An opioid antagonist (eg, naloxone-based) will be readily available for immediate intravenous administration at the discretion of the Investigator; subjects requiring naloxone rescue will be discontinued from the study.

Multiple-Dose Phase

At the end of the Single-Dose Phase for each age group, the IDMC will make recommendations for up to 3 dose levels to be used in the Multiple-Dose Phase. The Multiple-Dose Phase will proceed using the same age group stratification used in the Single-Dose Phase:

- A. 6 years to \leq 12 years
- B. 2 years to $<$ 6 years

Age groups A and B will be studied in parallel. Following postoperative parenteral analgesia, when oral dosing is to commence according to each institution's SOC, dosing will begin at the lowest dose selected by the IDMC based on results from the Single-Dose Phase for each age group. Subjects will be dosed every 4 to 6 hours (no sooner than every 4 hours and no later than every 6 hours) for up to 48 hours. Subjects may receive non-oxycodone, non-oxymorphone rescue medication and discontinue from the study in the event that the study drug does not provide adequate pain relief.

[figure not shown]

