In the Multiple-Dose Phase, the first treatment cohort of 6 subjects from each age group will be given multiple doses of oxymorphone HCl immediate-release oral liquid at an initial dose recommended by the IDMC following postoperative parenteral analgesia according to each institution's SOC. The IDMC will use data from each age group's Single-Dose Phase to recommend the dose(s) to be used in each respective age group's Multiple-Dose Phase. Following completion of the first treatment cohort of 6 subjects within each group, the effectiveness, safety, and tolerability will be assessed by an external IDMC. Following their review, the IDMC may recommend that a second treatment cohort of 6 subjects in each group be dosed with oxymorphone HCl immediate-release oral liquid at the second dose (recommended by the IDMC). Following review of the effectiveness, safety, and tolerability of the second treatment cohort within each age group, the IDMC may recommend that a third treatment cohort of 6 subjects in each age group commence (at the third dose recommended by the IDMC; the IDMC may at this point recommend to end the Multiple-Dose Phase of the study).

If needed, non-oxycodone, non-oxymorphone rescue analgesia will be available according to the SOC at each institution.

Blood from a patent line will be collected to assess pharmacokinetics, examine dose proportionality, and estimate effective and safe dosing. An opioid antagonist (eg, naloxone based) will be readily available for immediate intravenous administration at the discretion of the Investigator; subjects requiring naloxone rescue will be discontinued from the study.

The study design for EN3319-302 is illustrated in [Figure 1](#).

Figure 1: Study Design for EN3319-302

FOOTNOTES:

- ^a Up to 3 ascending dose levels for the Multiple-Dose Phase will be selected from the results of the Single-Dose Phase by the IDMC
- ^b Each subject will only be enrolled into one of the treatment cohorts in either the Single-Dose Phase or the Multiple-Dose Phase; a subject will not progress from one treatment cohort to the next treatment cohort.
- ^c Dose will be selected based on IDMC recommendation and review of the results of the 0.10 mg/kg cohort (if a dose other than 0.15 mg/kg or 0.20 mg/kg is selected by the IDMC, the dose must not exceed 0.30 mg/kg); the IDMC may also recommend to proceed directly into the Multiple-Dose Phase

IR=Immediate Release; q4-6=Every 4 to 6 hours; SOC=Standard of Care

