13. STATISTICS

13.1. Sample Size Consideration

The sample size of 6 subjects in each age group (A and B), treatment cohort, and study phase was selected to describe the safety, effectiveness and pharmacokinetic properties of the study drug in children aged 2 to ≤ 12 years. With up to 3 treatment cohorts and 6 subjects per treatment cohort, up to 18 subjects will be enrolled in each study phase. Assuming the %CVs for clearance and volume of distribution are both as high as 72% for pediatric subjects, then with 18 subjects per age group or 36 subjects per study phase, the 2-sided 95% confidence interval (CI) for both clearance and volume of distribution is $(0.71*X, 1.40*X)$, where X represents the geometric mean of either clearance or volume of distribution, respectively. In other words, with 18 subjects per age group or 36 subjects per study phase, the 2-sided 95% CIs are within 60% and 140% of the point estimates for the geometric mean estimates of both clearance and volume of distribution for oxymorphone in all age groups.

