13.5. Safety and Tolerability Analysis

Assessment of safety and tolerability will be based on the incidence of AEs, AEs resulting in discontinuation, and SAEs. Adverse events will be coded using the Medical Dictionary for Regulatory Activities (MedDRA). Summaries of AEs will be provided showing the number and percentage of subjects who experience at least 1 AE. These summaries will be presented by system organ class and preferred term. The occurrence of AEs will also be tabulated by severity. SAEs and AEs resulting in discontinuation will be summarized separately.

Assessment of safety and tolerability will also be based on pharmacokinetic analysis (described in section 13.6) clinical laboratory results, vital sign measurements, respiratory and neurological assessments, and other safety variables, which will be summarized by age group, treatment cohort, and study phase for each time point using appropriate descriptive statistics.

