13.6. Pharmacokinetic Analysis

Pharmacokinetic variables (Single-Dose Phase: C_{max} , T_{max} , C_{12} , AUC_{0-t} , AUC_{0-24} , $AUC_{0-\infty}$, λ_n , $t_{1/2}$, CL/F, and V/F; Multiple-Dose Phase: C_{max} , T_{max} , AUC_{0-t} , λ_n , $t_{1/2}$, CL/F, and V/F) will be estimated from the plasma concentration data using standard non-compartmental methods. Actual sample times, rather than scheduled times, will be used in the computation of pharmacokinetic parameters. Plasma concentrations below limit of quantification (BLQ) will be set to zero in the computation of mean concentration values; however, BLQ concentrations between 2 non-BLQ concentrations will be set to missing. For the computation of pharmacokinetic variables, the BLQ concentrations prior to the first measurable concentration

will be set to zero and other BLQ concentrations will be set to missing. The definitions and methods of determination for each pharmacokinetic variable are summarized in [Table 7](#).

Pharmacokinetic variables (CL/F , V/F , λ_n , and $t_{1/2}$, and dose normalized C_{max} , C_{12} , AUC_{0-24} , AUC_{0-t} , $AUC_{0-\infty}$) will be summarized by age group using N, mean, standard deviation (SD), geometric mean, CV, minimum, median, and maximum following dosing in the Single-Dose Phase and the first and third doses in the Multiple-Dose Phase. In addition, a 2-sided 95% CI will be constructed for both CL/F and V/F . T_{max} will be summarized by age group using median, minimum, and maximum.

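### PK blood is drawn to examine dose proportionality, but section 13.6 groups PK by age only and plans no dose-level comparison or slope; section 13.5 can be read otherwise

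*Combined protocol and SAP*

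**What the plan says.** Section 7 gives the purpose of sampling for each phase. Blood in the Single-Dose Phase "will be collected to assess pharmacokinetics, examine dose proportionality, and estimate effective and safe dosing", and the Multiple-Dose Phase text repeats this; the synopsis does the same for both phases. The single doses are 0.05, 0.10 and then 0.15 or 0.20 mg/kg, or another dose up to 0.30 mg/kg, with 6 children per cohort in each age group.

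Section 13.6 sets the PK output. CL/F, V/F, the terminal rate constant and half-life, "and dose normalized" Cmax, C12 and AUCs, "will be summarized by age group using N, mean, standard deviation (SD), geometric mean, CV, minimum, median, and maximum". Tmax is also given by age group. The only interval is for clearance and volume: "In addition, a 2-sided 95% CI will be constructed for both" CL/F and V/F. Section 13.1 states the precision of those two quantities for 18 children per age group or 36 per phase.

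Section 13.5 lists the PK analysis, with a pointer to 13.6, among the bases for judging safety and tolerability. The list ends: "which will be summarized by age group, treatment cohort, and study phase for each time point using appropriate descriptive statistics". The synopsis has the same sentence.

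**The concern.** Dividing Cmax and AUC by dose and then summarising over all cohorts in an age group takes proportionality as given. Proportionality can be seen only by setting the dose-normalised values of the cohorts side by side, or by estimating how exposure rises with dose. Section 13.6 names neither, and no dose-level PK comparison appears elsewhere in the supplied text. Disposition, demographics, effectiveness and the other safety data are all split by treatment cohort, so the omission in 13.6 stands out.

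The secondary objectives are to characterise the PK profile and to establish dosing recommendations. Carrying one CL/F value across mg/kg doses relies on proportionality. CL/F is dose divided by AUC, the reciprocal of dose-normalised AUC, so its pooled mean and CI carry the same assumption.

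**Working it through.** **The plan's own figure.** Section 13.1 gives a 95% CI of (0.71·X, 1.40·X) for the geometric mean: "Assuming the %CVs for clearance and volume of distribution are both as high as 72% for pediatric subjects". Using 0.72 as the log-scale SD, the normal quantile and n = 18:

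exp(±1.96 × 0.72/√18) = (0.717, 1.395).

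This agrees to within 0.01. With n = 36 the same formula gives (0.790, 1.265), which does not match. The stated precision therefore corresponds to about 18 children, that is, three cohorts of 6 pooled within an age group. This supports reading 13.6 as pooled over doses, although 13.6 does not say so outright.

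**What pooling would hide.** Suppose AUC is proportional to dose^1.3 over 0.05, 0.10 and 0.20 mg/kg with equal cohorts. The slope of 1.3 is illustrative.
- Dose-normalised geometric means relative to 0.05 mg/kg: 1.00, 2^0.3 = 1.23 and 4^0.3 = 1.52.
- Pooled geometric mean: 1.23. This equals the middle dose, is 23% too high for the lowest, and is 19% too low for the highest (1.23/1.52 = 0.81).
- Log-scale variance within a dose: ln(1 + 0.72²) = 0.418, so the SD is 0.646.
- Added variance between doses: (2/3)(0.3 × ln 2)² = 0.029. Total: 0.446.
- Pooled CV: √(exp(0.446) − 1) ≈ 75%, against 72% with no departure.

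A 1.5-fold trend would therefore show in the pooled table only as a CV about 3 points higher.

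**What the missing analyses could deliver.** The figures below assume that the 72% CV, stated for clearance and volume, also holds for Cmax and AUC.
- Geometric mean by cohort, n = 6, t with 5 df: 95% CI (0.51·X, 1.97·X).
- Slope b in ln(PK) = a + b·ln(dose), with b = 1 for proportionality. The half-width is t(0.975) × 0.646/√Sxx, with n − 2 df in one age group, and n − 3 df with both groups and an age term.

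| Doses (mg/kg) | Sxx, n = 18 | Half-width, n = 18 | Sxx, n = 36 | Half-width, n = 36 |
|---|---|---|---|---|
| 0.05/0.10/0.15 | 3.70 | ±0.71 | 7.41 | ±0.48 |
| 0.05/0.10/0.20 | 5.77 | ±0.57 | 11.53 | ±0.39 |

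With a top dose of 0.30 mg/kg the half-widths are ±0.44 (n = 18) and ±0.30 (n = 36). With only the 0.05 and 0.10 cohorts in one age group, the half-width is ±1.20.

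**The case against.** Section 13.5 is the best answer to this point. On its grammar, PK is among the items summarised by treatment cohort, so a reader who infers that no PK output at all will be split by dose goes further than the documents allow. That objection stands as far as it goes. But 13.5 sends the reader to 13.6 for the PK analysis, 13.6 names age group alone, and neither section plans a proportionality estimate. The two sections still have to be reconciled.

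Proportionality is also not a listed objective. It is a purpose of sampling, and the protocol promises only to examine it, without a test or criterion. This limits the weight of the point. A reader might infer that the trial cannot answer the question. That is too strong: the concentrations will exist, dose-normalised exposure and CL/F are the right quantities, and showing them by cohort would give a descriptive answer.

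A reader might also infer that, without proportionality, the pooled values apply to no studied dose. In the example above the pooled geometric mean equals the 0.10 mg/kg value; only the two outer doses are misstated. Nor does anything in the visible text suggest that exposure is non-proportional.

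Finally, the slope would be imprecise. With a top dose of 0.15 or 0.20 mg/kg, all four half-widths exceed the illustrative departure of 0.3; even with 36 children, an estimate of 1.3 would carry an interval of about 0.91 to 1.69 at best. This stands, and is why the slope should be an estimate and not a test.

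**Conclusion.** The gap is real but moderate. Followed as written, section 13.6 would leave a stated reason for sampling children unexamined, and sections 13.5 and 13.6 disagree on the grouping of PK results. The pooled summary would misstate the lowest and highest doses if exposure were not proportional, and its CV would give almost no warning: 72% to about 75% for a 1.5-fold difference.

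That pooling is intended is an inference from the age-only grouping, the dose normalisation and the 18 per age group. The slope precision assumes the 72% CV for Cmax and AUC, three full cohorts with evaluable PK and, for n = 36, the same doses and a common slope in both age groups. No slope precision can be given for the Multiple-Dose Phase, because the monitoring committee sets those doses.

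**What to change.** - **Grouping.** In section 13.6, summarise the PK variables by age group and treatment cohort, within each phase. Keep the pooled dose-normalised summary as secondary. Bring sections 13.5 and 13.6 and the synopsis into line.
- **Single-Dose Phase.** Regress log(Cmax) and log(AUC0-∞) on log(dose) with age group as a fixed effect. Report the slope with its 95% CI as an estimate, and state the expected half-width.
- **Multiple-Dose Phase.** Give the by-cohort summary. Fit a slope only if the doses chosen by the committee allow it. First reconcile the dosing occasions: 13.6 summarises the first and third doses, while section 12.4.1 places serial post-dose samples after Doses 1 and 7. Also name the AUC to be used, because the dosing interval varies from 4 to 6 hours and AUC0-t can cover different lengths of time in different children.

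The cost is a few extra tables and one regression. No new data are needed, and section 12.4.3 already batches samples by age group and treatment cohort.

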6.2. Secondary Objectives

The secondary objectives are: 1) to characterize the pharmacokinetic profile of oxymorphone HCl immediate-release oral liquid in children aged 2 to ≤ 12 years requiring an opioid to treat their acute postoperative pain of various etiologies; and 2) to establish the appropriate dosing recommendations for oxymorphone HCl immediate-release oral liquid in children aged 2 to ≤ 12 years requiring an opioid to treat their acute postoperative pain of various etiologies.

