Rescue medication ⁿ		As Needed Throughout Study																		
Convert subject to discharge opioid of Investigator's choice																			X	
Schedule 14day follow-up call with site																			X	
Study Completion																				X

FOOTNOTES:

Abbreviations: BL=Baseline; EOS=End-of-Study; ET=Early Termination; IRB=Institutional Review Board; PK=Pharmacokinetic; Pre-Op=Preoperative; Intra-op=Intraoperative

^a Tests results must be available for assessment by the Investigator, or designee, prior to dosing a subject.

^b Investigator, or designee, will train/retrain subjects, parent(s)/legal guardian(s) on the proper use and completion of the pain assessments.

^c Investigator, or designee, will assess if the subject has the cognitive ability to correctly complete the required pain assessments.

^d Pregnancy test (for females of child-bearing potential only) must be completed and the result assessed prior to administration of study drug. Serum βhCG at screening; urine pregnancy test before study drug administration, except if screening occurs in hospital.

^e Dosing times (see section 12.4.1) will vary depending upon the dosing interval.

^f Blood sample drawn before dosing study drug. Maximum number of blood samples for PK is 15 (Appendix E).

^g Clinical labs drawn as part of the SOC will be acceptable for study purposes. Intraoperative labs are acceptable provided they are drawn prior to first surgical incision and assessed by the Investigator prior to administration of the first dose of study drug.

^h Captured following execution of informed consent/assent.

ⁱ Collected by the Investigator for up to 14 days after the last dose of study drug (**documented telephone follow-up required**).

^j See Appendix B and section 9.3 for concomitant medication reporting.

^k A pain assessment will also be completed at the time of rescue immediately prior to rescue medication administration. **No pain assessments will be completed beyond rescue.**

^l Must include type of procedure(s), date of procedure(s), surgical start/stop time, and anesthesia/analgesia start and stop time.

^m Record all times that any food was consumed and what food was consumed (Diet-as-tolerated [DAT], DAT-soft, Full Fluids, Clear Fluids, water) by the subject from 1h prior to dosing through to EOS at 48h post 1st dose/ET.

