12.4. Pharmacokinetic Assessments

12.4.1. Blood Sample Collections

Blood collection may be performed using an existing line (arterial or venous noted on eCRF) at the start of the study (the use of EMLA[®] at the insertion site is permitted). If access for blood sampling is lost, a new line will only be established as part of the clinical management of the subject; otherwise, the subject's participation in the study will be early terminated. Procedures for blood draws should follow institutional SOC. All catheter lines should be appropriately flushed per institutional SOC prior to each blood draws. The discard volume must be restricted to 0.5 mL for tubing with a dead space of ≤ 0.5 mL and up to 1.0 mL for tubing with a dead space > 0.5 mL. Calculation and evaluation of the following pharmacokinetic variables will be performed for all subjects participating in study: (Single-Dose Phase: C_{max} , T_{max} , AUC_{0-t} , AUC_{0-24} , $AUC_{0-\infty}$, λ_n , $t_{1/2}$, CL/F [clearance], and V/F [volume of distribution]; Multiple-Dose Phase: C_{max} , T_{max} , AUC_{0-t} , λ_n , $t_{1/2}$, and CL/F; see [Table 7](#) for definitions). Blood samples (0.5 mL) will be obtained and placed into 2.0-mL dipotassium ethylenediaminetetraacetic acid (K₂EDTA) tubes at each blood collection time point for both phases (see [Table 3](#) and [Table 4](#)). The samples will be obtained at the following times:

- Single-Dose Phase: Serial blood will be collected at time 0 (Baseline), at 15 and 30 minutes, and at 1, 1.5, 2, 4, 6, 8, 12, and 24 hours post dose.
- Multiple-Dose Phase: Serial blood will be collected at: 0 (Baseline), at 0.5, 1, 1.5, and 2 hrs post-Dose 1, immediately prior to Doses 2, 3, 4, 5, 6, 7, and at 0.5, 1, 1.5, and 2 hrs post Dose 7.

Table 7: Pharmacokinetic Variables

Variable	Definition
C_{\max}	Maximum plasma concentration; the highest concentration observed during a dosage interval
T_{\max}	The time at which C_{\max} was observed
AUC_{0-t}	Area under the concentration versus time curve from time 0 to the last measured concentration (C_t) in the dosing interval, calculated by linear trapezoidal rule
$AUC_{0-\infty}$	Area under the concentration versus time curve from time 0 to infinity, calculated as $AUC_{0-t} + C_t/\lambda_n$
AUC_{0-24}	Area under the concentration versus time curve from time 0 to 24 hours (end of dosing interval)

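### Multiple-Dose PK profiles are drawn after Doses 1 and 7, but 13.6 reports Doses 1 and 3 and plans no within-child accumulation ratio and no trough that fits 4-6 h dosing

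*Combined protocol and SAP*

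**What the plan says.** Sections 7.1.5 and 12.4.1 set the Multiple-Dose sampling: baseline; 0.5, 1, 1.5 and 2 h after Dose 1; then "immediately prior to Doses 2, 3, 4, 5, 6, 7, and at 0.5, 1, 1.5, and 2 hrs post Dose 7". Table 4 agrees: "Maximum number of blood samples for PK is 15", which is 1 + 4 + 6 + 4.

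Section 13.6 and the Synopsis list Cmax, Tmax, AUC0-t, the terminal rate constant, half-life, CL/F and V/F for this phase. The variables "will be summarized by age group using N, mean, standard deviation (SD), geometric mean, CV, minimum, median, and maximum", after the single dose and after the first and third doses of the Multiple-Dose Phase. Confidence intervals are planned for CL/F and V/F only. C12, the one variable defined as a trough, belongs to a 12-hour interval and is listed for the Single-Dose Phase, though it reappears in the pooled summary list. The BLQ rules in 13.6 refer to mean concentrations, but no summary of pre-dose concentrations is specified.

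A secondary objective (6.2) is "to establish the appropriate dosing recommendations for oxymorphone HCl immediate-release oral liquid". Section 13.5 bases part of the safety assessment on the PK analysis.

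**The concern.** Whether exposure rises under repeated dosing every 4 to 6 hours is the PK question this phase is placed to answer, and it bears on the dosing objective. The sampling suits it: the same child is sampled at the same post-dose times after two doses six intervals apart, with pre-dose levels in between.

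The analysis does not follow the sampling. For Dose 3 there is a sample just before it and the next is just before Dose 4, so a Cmax, Tmax or terminal slope cannot usefully be estimated. Dose 7, the only later dose with a profile, is absent from the summary. If the plan is followed as written, the Dose 7 profile goes unreported. If Dose 7 were simply added as another group summary, a reader would have to compare two sets of group statistics and carry the full between-child spread, although each child can serve as his or her own control.

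**Working it through.** **Inputs from the plan (13.1).** "Assuming the %CVs for clearance and volume of distribution are both as high as 72% for pediatric subjects"; "with 18 subjects per age group or 36 subjects per study phase"; two-sided 95% level; and a stated standard that the intervals "are within 60% and 140% of the point estimates".

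**Inputs assumed.** The 72% is stated for CL/F and V/F; I apply it to Cmax and AUC over 0-2 h. Within-child CV is not given; I use 20-40%. Half-life and absorption rate are not given; they enter only the illustrations at the end.

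**Reproducing the plan's figure.** The plan gives (0.71, 1.40) times the geometric mean. With 72% used directly as the log SD and a normal quantile, exp(±1.96 × 0.72/√18) = (0.717, 1.395). With log SD = √ln(1 + 0.72²) = 0.646 and a t quantile, the result is (0.725, 1.379). Both are close to the stated interval, so it belongs to n = 18. At n = 36 the first method gives (0.79, 1.27). I use 0.646 below.

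**Dose 7/Dose 1 ratio, 95% CI factor.**
- Unpaired, two group summaries treated as independent: exp(t(2n−2) × 0.646 × √(2/n)). At n = 18: exp(2.032 × 0.646 × 0.333) = 1.55.
- Paired, log differences within child: exp(t(n−1) × s_w × √(2/n)), with s_w = √ln(1 + CV_w²), that is 0.198, 0.294 and 0.385 for CV_w of 20%, 30% and 40%. At n = 18 and 20%: exp(2.110 × 0.198 × 0.333) = 1.15.

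| n | Unpaired | Paired, 20% | Paired, 30% | Paired, 40% |
|---|---|---|---|---|
| 18 (full age group) | 1.55 | 1.15 | 1.23 | 1.31 |
| 12 | 1.73 | 1.19 | 1.30 | 1.41 |
| 6 (one cohort) | 2.30 | 1.34 | 1.55 | 1.77 |

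Taking the plan's upper limit of 1.40 as a yardstick, the unpaired comparison at n = 18 misses it. The paired one meets it up to a within-child CV of about 51% at n = 18, 39% at n = 12 and 23% at n = 6.

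**Power at n = 18 (noncentral t, two-sided 5%).**

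| True ratio | Unpaired | Paired, CV_w 30% |
|---|---|---|
| 1.25 | 17% | 58% |
| 1.5 | 45% | 97% |
| 2.0 | 88% | >99% |

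**Why the two doses need a common window.** AUC0-t runs to the last measured concentration in the dosing interval. After Dose 1 that is the sample before Dose 2, at 4-6 h. After Dose 7 it is 2 h, because 7.1.5 lists no sample before Dose 8. Take rapid absorption, a half-life of 2 h and dosing every 4 h. True accumulation is 1/(1 − 0.25) = 1.33. The first 2 h hold 0.5 of a single-dose AUC and the first 4 h hold 0.75, so the AUC0-t ratio would be 1.33 × 0.5/0.75 = 0.89, and the build-up would not show.

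**Limit of the 0-2 h window.** For an oral one-compartment model with the same half-life and interval and an absorption rate of 1/h, evaluated at the scheduled times, the AUC0-2h ratio at Dose 7 is 1.83, against 1.59 for the full interval. AUC0-2h exceeded the full-interval ratio in every case tried (half-life 2-10 h, absorption rate 0.75-4/h).

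**The case against.** The case on the other side has several parts.

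- *The unpaired Dose 7 comparison is not in the plan.* Correct. Section 13.6 summarises Dose 3, so the factor of 1.55 describes what a reader would face if Dose 7 were added as a separate summary. The mismatch between sampled and reported doses comes first.
- *Not every child gives both profiles.* A reader might infer this from the schedule. The documents do not support it: children may discontinue for inadequate relief, and loss of the sampling line ends participation unless a new line is placed for clinical care. Dose 7 falls 24-36 h after Dose 1. No dropout rate is given, and the IDMC may stop before three cohorts, so 18 is a maximum.
- *The phase can still answer the question.* A reader might infer that it cannot. The samples are collected, a ratio remains derivable, and mean pre-dose concentrations are not excluded. The weakness is in the planned outputs.
- *The gain depends on the true ratio.* At n = 18 an unpaired interval already excludes 1 for any observed ratio above 1.55. At an observed ratio of 1.14, even the paired interval at 20% CV includes 1. The benefit of pairing is largest between those values.
- *The early-window ratio is not a pure accumulation index.* This stands. It can exceed full-interval accumulation. Food is unrestricted and its effect in children unstudied, so a change in diet or absorption between Doses 1 and 7 would also move it.
- *The study is descriptive, so this is a preference.* Only in part. A paired geometric mean ratio is itself descriptive, and reporting a dose without a profile while omitting the one that has it is an inconsistency.

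**Conclusion.** The point holds for the planned outputs. Section 13.6 and the Synopsis report doses that do not match the sampling, and they contain no within-child accumulation measure and no trough suited to 4-6 h dosing. At n = 18 per age group, pairing would narrow the 95% CI factor from 1.55 to between 1.15 and 1.31; with 12 completers the paired factor is 1.19 to 1.41. These sizes rest on carrying the 72% CV over to Cmax and AUC0-2h and on an assumed within-child CV of 20-40%. A two-fold build-up would probably show even unpaired (88% power); one of 1.25 to 1.5 probably would not (17% to 45%). The change is worth making before database lock.

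**What to change.** In 13.6 and the Synopsis:

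1. Reconcile the reference to the third dose with the Dose 1 and Dose 7 profiles in 7.1.5, 12.4.1 and Table 4.
2. For children sampled through 2 h after Dose 7, prespecify the within-child Dose 7/Dose 1 ratio of Cmax (observed over 0-2 h) and of AUC0-2h. Report each by age group as a geometric mean ratio with a 95% CI from paired log differences, and state the number of children contributing.
3. Label these as early-window exposure ratios that can exceed full-interval accumulation and may reflect changes in food or absorption.
4. Summarise dose-normalised pre-dose concentrations for Doses 2 to 7 by dose number, using actual times since the previous dose, with a stated BLQ rule that also works on the log scale. A log-scale mixed model with child as random effect is optional; the pre-dose summary also uses children who leave before Dose 7.

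The cost is protocol wording and about two tables, with no extra blood or children. The downside is that the ratio describes only children who reach Dose 7 with a working line, who may differ from those who leave early.
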